3.3 Study Duration, Enrollment and Number of Sites

3.3.1 Duration of Subject Study Participation

For the qualitative phase, the study duration will last one day. For the field testing, the study duration per subject will be up to 3 months. For the RCT, the study duration per subject will be up to 8 months, with up to 1 month screening, up to 6 months for baseline assessments and intervention delivery, and 2 months for study visits completion.

3.3.2 Total Number of Study Sites/Total Number of Subjects Projected

The study will be conducted at approximately 1 investigative site at CHOP in the United States.

Recruitment for RCT will stop when approximately 100 participants (50 youth-caregiver dyads) are enrolled. It is expected that approximately 100 subjects will be enrolled to produce 85 evaluable subjects. Recruitment for interviews will stop when approximately 30 participants (15 youth-caregiver dyads) are enrolled and recruitment for field testing will stop when approximately 10 (5youth-caregiver dyads) are enrolled.

3.4 Study Population

3.4.1 Inclusion Criteria

3.4.1.1 Youth Inclusion Criteria for qualitative interviews

- 1) Identify as Black
- 2) are between ages of 10-18 years
- 3) endorse suicidal ideation and/or behaviors within the last year at an ED visit
- 4) live within Philadelphia County or nearby Pennsylvania suburb
- 5) Must be able to read and understand English

3.4.1.2 Youth Inclusion Criteria for field testing and RCT

- 1) Identify as Black
- 2) Are between ages of 10-18 years
- 3) Endorse suicidal ideation and/or behaviors within the last year at an ED visit
- 4) Live within Philadelphia County or nearby Pennsylvania suburb

- 5) Must be able to read and understand English

3.4.1.3 Caregiver Inclusion Criteria for interviews, field testing, and RCT

- 1) Parent or legal guardian of eligible youth
- 2) Must be able to read and understand English

3.4.1.4 Patient Navigator Inclusion Criteria for RCT

- 1) Employed by study to implement adapted STAT-ED

3.4.2 Exclusion Criteria

- 1) Does not identify Black as one of their races
- 2) Under 10 or over 18 years old
- 3) Does not speak English
- 4) No history of suicidal ideation or behavior

3.4.2.1 Youth Exclusion Criteria for interviews

- 1) Exclusion criteria listed in section 3.4.2
- 2) Requires acute or intensive inpatient treatment for safety or medical reasons

3.4.2.2 Youth Exclusion criteria for field testing

- 1) Exclusion criteria listed in section 3.4.2
- 2) Requires acute or intensive inpatient treatment for safety or medical reasons
- 3) Currently engaged in mental health treatment

3.4.2.3 Youth Exclusion criteria for RCT

- 1) Exclusion criteria listed in section 3.4.2
- 2) Currently engaged in mental health treatment

3.4.2.4 Patient Navigator Exclusion Criteria

- 1) Does not consent to be a secondary research participant

Subjects with limited English proficiency will be excluded from this study because the interview materials and measures are not available in multiple languages. In addition, the adaptation and implementation of the intervention in multiple languages is not feasible for this pilot study. If this study shows efficacy, we will hope to be able to engage Black families who speak languages other than English in the next study.

Subjects that do not meet all of the enrollment criteria may not be enrolled. Any violations of these criteria must be reported in accordance with IRB Policies and Procedures.

4 STUDY PROCEDURES

4.1 Screening Visit

Qualitative Interviews, Field Testing, and RCT

- Informed Consent/assent/HIPAA authorization
- Medical Record Review
- Review of Inclusion/Exclusion Criteria
- Collection of demographics including contact information

4.2 Study Treatment Phase

This will include the qualitative interviews, field testing, and RCT. Medical Health Record Review will not access protected mental health records.

4.2.1 Visit 1

Qualitative interviews

- Informed Consent/Accent
- Medical Record Review
- Review of Inclusion/Exclusion Criteria
- Recorded semi-structured interview
- Demographics questionnaire

Field Testing

- Review of Inclusion/Exclusion Criteria
- Informed consent/assent
- Demographics questionnaire
- Field testing procedures

RCT

- Medical records review
- Review of inclusion/exclusion criteria
- Youth and caregiver report measures (MYTS, SIQ-Jr, PANAS, demographics questionnaire)
- Randomization
- Intervention

4.2.2 Visit 2**RCT**

- Youth and caregiver report measures (MYTS, SIQ-Jr, ED STARS, AIM)
- Assess possible adverse events
- Medical Health Record Review

4.2.3 Visit 6: End of Study

The end of the study visit for randomized trial is at 6 months after baseline assessment. Youth and caregiver report measures are administered (MYTS, SIQ-Jr, ED STARS, intervention acceptability survey). Adverse events will be assessed.

4.3 Unscheduled Visits

If a family needs additional intervention support to navigate mental health initiation, then this will be performed by the patient navigators.

4.4 Subject Completion/Withdrawal

Subjects may withdraw from the study at any time without prejudice to their care. They may also be discontinued from the study at the discretion of the Investigator for lack of adherence to the study visit schedule or any AEs. The Investigator may also withdraw subjects who violate the study plan, or to protect the subject for reasons of safety or for administrative reasons. It will be documented whether or not each subject completes the study. If the Investigator becomes aware of any serious, related adverse events after the subject completes or withdraws from the study, they will be recorded in the source documents and on the CRF.

4.4.1 Early Termination Study Visit

If early termination occurs, reasons for early termination will be documented.

Subjects who withdraw from the study or were withdrawn from study before or during the intervention will be asked to complete the post-intervention assessments. Subjects who withdraw prior to the baseline assessment will be considered lost and not be evaluable.

5 STUDY EVALUATIONS AND MEASUREMENTS

5.1 Screening and Monitoring Evaluations and Measurements

5.1.1 Medical Record Review

Medical record number

Date of birth

Demographics including county of residence

Race

Columbia Suicide Severity Rating Scale

Behavioral Health Screen

Problem list

ICD codes

Contact information

Languages spoken/read

Results of tests and procedures

Chart review for mental health treatment or hospitalizations (this will be gathered from medical records and will not access protected mental health records)

Medical insurance information

5.1.2 Other Evaluations, Measures

Qualitative Interviews

- *Qualitative interview guide* will be developed. Questions concerning perceptions and preferences of mental health treatment and barriers and facilitators to accessing mental health services will be asked of participants.
- *Demographics survey* will gather information such as age, biological sex, gender, race/ethnicity, sexual orientation, and family income.

Field Testing

- *Demographics survey* will gather information such as age, biological sex, gender, race/ethnicity, sexual orientation, and family income.
- *Patient navigation notes*

RCT

- ED STARS mental health service use is a 8-item interview that measures mental health services children receive and actions taken by family to obtain services. This measure was used with over 6000 adolescents from the Pediatric Emergency Care Applied Research Network (PECARN) that spanned diverse geographic regions of the US (King et al., 2020). Caregivers will complete this interview unless youth is participating without a parent.
- *Motivation for Youth's Treatment Scale (MYTS)* is an 8-item measure of intrinsic treatment motivation that has both youth and parent reports (Breda et al., 2012). It has two subscales: recognition that the youth has a problem and readiness to participate in the youth's treatment. It has good internal consistency and validity with support for the factors. MYTS has a 5-point Likert scale with higher scores representing higher motivation. MYTS will be completed by youth and caregivers.
- *Suicide Ideation Questionnaire-Junior (SIQ-Jr)* is a youth report measure of frequency of suicidal thoughts over the last month (Reynolds, 1988). SIQ-Jr has high internal consistency, test-retest reliability, predictive validity for suicidal behavior, and is sensitive to change (Reynolds & Mazza, 1998).
- Acceptability of Intervention Measure (AIM), a 4-item, psychometrically-validated measure that indexes the extent to which stakeholders believe an intervention is acceptable. Both youth and a caregiver will rate the intervention helpfulness and satisfaction. Additionally, the patient navigator will complete the AIM after the trial is completed.
- *Positive and Negative Affect Scale (PANAS)* is a widely used and validated measure (Watson et al., 1988). It has been used for adolescent samples with evidence of potentially three factors: Positive Affect, Negative affect with two factors of Distress and Fear (Villodas et al., 2011; Allan et al., 2015). The Positive Affect factor will be administered to youth.
- *Demographics survey* will gather information such as age, biological sex, gender, race/ethnicity, sexual orientation, family income, religion, and insurance type. Same demographic survey will be used for interviews and field testing. Another demographic survey will be used for RCT.
- Feasibility of Intervention Measure (FIM), a 4-item, psychometrically-validated measure that indexes the extent to which stakeholders believe an intervention is feasible. The patient navigator will complete the FIM after the trial is completed.

A *fidelity checklist* has been developed to assess self-reported task completion by the patient navigators (0- not completed, 1- partially completed, 2- fully completed). This will be completed after the interview.

5.2 Efficacy Evaluations

In the RCT, these are the measures that will be used to assess efficacy (mental health utilization)- ED STARS. The three primary efficacy outcomes are 1) whether the patient initiated mental health treatment (yes/no), 2) time to treatment initiation, and 3) number of

treatment sessions attended. Other outcomes are suicidal ideation and behavior measured by SIQ-Jr.

5.2.1 Diagnostic Tests, Scales, Measures, etc.

In the qualitative interviews, the research staff will conduct semi-structured interviews with questions concerning perceptions and preferences of mental health treatment and barriers and facilitators to accessing mental health services with youth and caregiver participants. In the field testing, participants will not complete any measures or scales. . In the RCT, ED STARS is an interview and will be administered by research staff to caregivers at 2 (Study visit 2) and 6 months (final visit) after baseline assessment. SIQ-Jr is a self-report measure that will be administered to youth at baseline and 2 and 6 months after baseline assessments.

5.3 Safety Evaluation

In the RCT, participant safety will be monitored by adverse events and the SIQ-Jr. It will also include responses on the intervention satisfaction.

6 STATISTICAL CONSIDERATIONS

6.1 Primary Endpoint

Primary endpoint for qualitative phase (interviews and field testing): themes of caregiver and youth mental health attitudes and engagement and an adapted STAT-ED manual
Primary endpoint for randomized trial: mental health treatment initiation. The three primary efficacy outcomes are: a) whether the patient initiated mental health treatment (yes/no), b) time to treatment initiation, and c) number of treatment sessions attended.

6.2 Secondary Endpoints

At the end of the RCT, we will also solicit and review feedback from the patient navigators about feasibility and acceptability and evaluate fidelity by calculating an overall adherence to intervention tasks score for each patient navigator by aggregating navigator ratings on the fidelity checklist. Both youth and caregiver will complete AIM.

6.3 Statistical Methods

6.3.1 Baseline Data

For qualitative interviews, caregiver and youth interviews will be analyzed using EHOST open source analysis software. Initial codes will be developed inductively through investigative team consensus. Themes pertaining to child, family, clinician and systemic barriers and facilitators, motivation for treatment, receipt and perceptions of mental health services will be identified. After initial exploration, a comprehensive coding scheme will be developed and applied to all data to produce a fine-grained descriptive analysis.

For the RCT, descriptive statistics for demographic and behavioral characteristics measured at baseline will be examined across the two treatment groups to assess the success of the randomization.

6.3.2 Efficacy Analysis

These are the measures that will be used to assess efficacy (mental health utilization), ED STARS. The three primary efficacy outcomes are 1) whether the patient initiated mental health treatment (yes/no), 2) time to treatment initiation, and 3) number of treatment sessions attended. Other outcomes are suicidal ideation and behavior which will be examined by changes in total score over time from baseline to Visit 2 and final Visit.

6.3.3 Safety Analysis

In the RCT, Participant safety will be monitored by adverse events reporting. Participant safety will be monitored by adverse events and the SIQ-Jr. It will also include responses on the intervention satisfaction.

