The study will recruit from CHOP pediatric hospital ED with a total of 151 participants (75 youth, 75 caregivers, and 1 patient navigator). Eligible youth will identify as Black, be between the ages of 10-18, have recent or past suicidal ideation or behaviors and are not currently receiving mental health treatment. Caregivers are parents or legal guardians of eligible youth. Patient navigator will be hired patient navigator who consents to being a secondary research participant. Study procedures may be conducted in-person, over the phone, or online.

[figure not shown]
Study Interventions and Measures:

Participants will be randomized to the adapted STAT-ED or enhanced Treatment as Usual which will consist of follow up telephone contacts following discharge from the ED. Main RCT study outcomes are mental health treatment initiation and suicidal ideation.

Table 1: Schedule of Study Procedures for Randomized Controlled Trial

Study Phase	Screening	Observation Study Visits		
Visit Number		Baseline	2 month follow up	6 month follow up
Informed Consent/Assent	X			
Review Inclusion/Exclusion Criteria	X	X		
MYST		X	X	X
SIQ-Jr		X	X	X
Demographics		X		
PANAS		X		
AIM			X	X
ED STARS			X	X
Adverse Event / Unanticipated Problems Assessment		X	X	X

Figure 1: Flow Diagram for RCT

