1.2 Name and Description of Investigational Product or Intervention

Patient navigation will generally be modeled after STAT-ED and can involve motivational interviewing, brief case management, and telephone contacts. While the complete intervention is contingent on our adaptations, we anticipate that the following strategies will be included: psychoeducation, problem-solving logistical barriers, and assistance with making and following up with mental health appointments (Godoy et al., 2019). As part of the cultural adaptation, we will directly address youth's and caregivers' negative perceptions and cultural stigma concerning mental health treatment. Psychoeducation will be provided on suicide risk, its negative effects, and treatment options. The intervention will assist the family in following up with mental health referral recommendations provided by ED staff and eliciting families' preferences in regards to race and gender of providers, convenience of provider, and type of treatment. This assistance could involve help with the initial telephone contact, getting to appointments, and preparing for the appointments. The patient navigator will communicate with the family in person, by telephone, and/or by text messaging as per family's preference. This once to twice a week communication will promote mental health care initiation and identify barriers and problem-solving solutions. The intervention group is expected to be administered the adapted STAT-ED until the first mental health appointment

date. A comparison intervention (enhanced Treatment as Usual) will consist of follow up contacts following discharge from the ED to confirm referral recommendations.

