RCT: Study staff will contact enrolled participants, complete baseline assessments, and randomize to the adapted STAT-ED or control condition (enhanced Treatment as Usual). The adapted STAT-ED will involve the following strategies: psychoeducation, motivational interviewing, problem solving logistical barriers, and assistance with making and following up with mental health appointments. This could involve identifying additional mental health resources and providers based on insurance type. One social worker has been hired and trained to implement the adapted STAT-ED and the control condition (enhanced Treatment as Usual) for study. Patient navigator will communicate with the family in person, by telephone, and/or by text messaging via family's preference. The control condition (enhanced Treatment as Usual) will receive telephone contacts to check in and remind families about mental health care initiation. Telephone contacts are consistent with current ED practice in which social work team members follow up by telephone with patients and their caregivers about referrals given at ED discharge. The proposed study is a small pilot to adapt a patient navigator intervention for suicidal Black youth and test the preliminary effectiveness of the intervention in preparation for a fully-powered RCT. We will perform initial analyses (chi-square and *t*-tests) to compare the intervention and control groups on proportion to initiate mental health treatment, mean number of days to treatment initiation, and mean number of treatment sessions at both 2 months and 6 months follow-up. A Cox proportional hazards model will examine group differences in mental health utilization, time to treatment initiation, suicidal ideation, and mental health motivation (Cox, 1972). Assessments may be conducted in-person, via telephone, or electronically/online. At the end of the study, we will also solicit and review feedback from the patient navigator who is research staff member about feasibility and acceptability. The patient navigator will also complete fidelity measure after first session of the adapted STAT-ED.

Participants may be recontacted to update information or to see if they are interested in participating in other research.

3.2 Allocation to Treatment Groups and Blinding.

In the RCT, subjects will be randomized to either the adapted STAT-ED or to enhanced treatment as usual. Randomization will be accomplished in advance using computer-

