7 SAFETY MANAGEMENT

7.1 Clinical Adverse Events

Clinical adverse events (AEs) will be monitored throughout the study.

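### Adverse-event counts by arm may partly reflect unequal contact, because the safety analysis does not separate events by how they were found

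*Combined protocol and SAP*

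**What the plan says.** Section 6.3.3 states "In the RCT, Participant safety will be monitored by adverse events reporting", then "Participant safety will be monitored by adverse events and the SIQ-Jr", and adds responses on intervention satisfaction. Section 7.1 sets the window: "Clinical adverse events (AEs) will be monitored throughout the study". Neither section says how events are elicited, from which source, or how they will be summarized by arm.

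Table 1 has a row "Adverse Event / Unanticipated Problems Assessment" marked at baseline, 2 months and 6 months, without distinction by arm. Sections 4.2.2 and 4.2.3 repeat the 2- and 6-month assessments.

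For the adapted STAT-ED arm, Section 1.2 says "This once to twice a week communication will promote mental health care initiation and identify barriers and problem-solving solutions" and "The intervention group is expected to be administered the adapted STAT-ED until the first mental health appointment" date. Section 3.3.1 allows up to 6 months for baseline assessment and intervention delivery together, and Section 4.3 permits extra navigator support on request.

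For the control arm, Section 3.1.2 says that it "will receive telephone contacts to check in and remind families about mental health care initiation". The number and spacing of these calls are not given. The same section says that one social worker delivers both conditions.

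**The concern.** When events can be recorded at any time, the arm with more conversations has more chances for an event to be mentioned. The content differs too: STAT-ED includes motivational interviewing and psychoeducation on suicide risk, whereas the control calls check in and remind. At equal true risk, more ideation, attempts or return ED visits could come to light under STAT-ED.

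The extra observation is also tied to the outcome. Navigation ends at the first appointment, and treatment initiation is the primary endpoint. Within STAT-ED, the youth watched longest are therefore those who have not started care.

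Any AE counts by arm that reach the DSMB (Section 8.4.1) or the ClinicalTrials.gov results (Section 9) could make the intervention look less safe than it is, or blur a real difference. Section 8.4.4 expects the pilot to give preliminary information on suicidal ideation and behavior for later studies, so a distorted count could carry forward.

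**Working it through.** The plan states no AE rate, detection rate or harm comparison, so there is no figure to reproduce. The check has three parts.

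**1. Contact opportunity.** At one to two contacts a week, 2 months (about 8.7 weeks) gives about 9 to 17 contacts, and 26 weeks gives 26 to 52. These are upper cases, for a youth who has not yet started care. The control figure is unknown.

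**2. Illustrative detection model with equal true risk.** These assumptions are not from the documents:
- Event onset is uniform over 26 weeks.
- If a navigator or control call follows onset, it elicits the event with probability c = 0.3.
- The next scheduled visit elicits it with probability s = 0.5, 0.8 or 1.0.
- L is the week of the last such contact in that arm.

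The share detected is D = s + (1 − s) × c × L/26. For example, with s = 0.5:
- STAT-ED, 8 weeks of navigation: 0.5 + 0.5 × 0.3 × 8/26 = 0.546
- Control, one call at week 1: 0.5 + 0.5 × 0.3 × 1/26 = 0.506
- Ratio: 0.546/0.506 = 1.08

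Ratios of detected events over 6 months, STAT-ED to control:

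| Navigation | Control calls | s = 0.5 | s = 0.8 | s = 1.0 |
|---|---|---|---|---|
| 4 weeks | 4, last at week 8 | 0.96 | 0.99 | 1.00 |
| 8 weeks | 4, last at week 8 | 1.00 | 1.00 | 1.00 |
| 8 weeks | 1, at week 1 | 1.08 | 1.02 | 1.00 |
| 16 weeks | 1, at week 1 | 1.17 | 1.04 | 1.00 |
| 26 weeks | 1, at week 1 | 1.29 | 1.07 | 1.00 |

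For events starting in the first 2 months, 8 weeks of navigation against one control call gives 1.23 (s = 0.5) or 1.06 (s = 0.8). Four weeks of navigation against four control calls gives 0.89 (s = 0.5).

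Only the next contact can elicit an event here, so weekly frequency drops out and 1.29 is not a ceiling. If each of four later contacts had an independent 0.3 chance, elicitation would be 1 − 0.7⁴ = 0.76.

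In events this is small. Assume 25 youth per arm (50 youth; the allocation ratio is not stated) and a true risk of 20%, so 5 affected youth per arm. The last row at s = 0.5 gives 5 × 0.650 = 3.25 detected against 5 × 0.506 = 2.53, a gap of 0.7. At 40% risk the gap doubles to 1.4.

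**3. Effect of the remedy.** If the comparison uses only events elicited at the shared visits, the share is s in both arms and the ratio is s/s = 1.00 at any contact frequency. This requires the same questions and equal attendance. Section 3.3.2 expects 85 evaluable of 100 participants. If that were visit attendance split as 90% and 80% (assumed), the ratio would be 0.90/0.80 = 1.125. A scheduled-visit summary should therefore not stand alone.

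**The case against.** The strongest reply is that no between-arm AE analysis is planned. Section 6.3.3 speaks of monitoring, Sections 7.2 and 8.4.1 foresee narrative or other summaries, and Section 6.4 says the pilot is not meant to detect significant differences. This stands. It confines the problem to descriptive counts but does not remove it, because those counts can still be read by arm.

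A reader might infer that control-arm events surface only through recall at the 2- or 6-month visit. The documents do not support that. Control families are called to check in, by the same social worker. Visit 2 includes a record review, and the SIQ-Jr is given to all RCT youth on one schedule. These sources do not fully equalize detection: the record review excludes protected mental health records (Section 4.2) and is not listed at the final visit (Section 4.2.3), and Section 5.1.2 describes the SIQ-Jr as covering suicidal thoughts over the last month.

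A reader might also infer that detection will certainly differ, or attach a large risk ratio by assuming detection rates for each arm. Neither is supported. Control-call frequency, actual navigation length and whether contacts elicit AEs are all unstated, and a ratio built from assumed detection rates only returns the assumption.

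Finally, the AE form is not among the documents, and the Appendix only refers to an attachment. A field for the source of each event may already exist. If so, only the text of 6.3.3 needs changing.

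**Conclusion.** The concern holds in a limited form. Contact intensity is unequal as written, AE collection is open-ended, and 6.3.3 has no rule separating events found during navigation from those asked about at the shared assessments. Counts by arm may therefore be affected by detection, most likely toward more events in STAT-ED.

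The size is not known. The model gives about 0.96 to 1.29 over 6 months, under assumed values for elicitation, navigation length and control calls. It could be nil or slightly reversed, and with more effective repeated contacts it could exceed 1.29. With 50 youth this may amount to about one event or less, but so few events are expected that even this can change how a table looks.

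No planned inference is invalidated. This is a worthwhile, low-cost improvement to descriptive safety reporting.

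**What to change.** On the AE form, record how each event was found: scheduled assessment, navigator or control call, chart, or spontaneous report.

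In 6.3.3, state that two summaries will be shown by arm:
- **(a) Like-for-like summary:** AEs elicited with the same questions in both arms at the 2- and 6-month assessments. The questions cover the whole interval since the last assessment and are asked whether or not the event is already known.
- **(b) Full summary:** all AEs by source, with the number of contacts and scheduled-visit attendance by arm.

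All events continue to be reported as Sections 7.2 and 8.4.1 already require, whatever their source.

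The cost is one form field and a few sentences, with no new visits or staff. Summary (a) omits events in youth who miss scheduled visits, possibly because of the event itself, which is why (b) belongs beside it.

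A separate editorial point: Table 1 marks an AE assessment at baseline, but the RCT list in Section 4.2.1 does not include one. The two should be reconciled.
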